5.2.4.2 Jump to reference method (J2R)

The J2R method will be applied to impute the post-withdrawal data for any subject assigned to BIIB092 treatment who withdraws from study early based on data from the placebo group rather than the subject's own randomized treatment group [Carpenter et al. 2013]. Specifically, for a subject assigned to BIIB092 treatment who withdraws early, his or her mean trajectory after early

withdrawal is assumed to be the same mean trajectory as the placebo group. This method assumes that any benefit gained from previous treatment will be immediately lost. For any subject on placebo who withdraws early, his or her post-withdrawal profile will be imputed following the missing-at-random principle. Implementation details can be found in Section 11.2.2.

After all missing data have been imputed, MMRM model described in Section 5.1 will be applied for analysis.

5.2.4.3 Imputed by natural disease progression

After early withdrawal from the study, subjects are assumed to exhibit an evolution of the disease similar as the natural disease progression (for all treatment groups) in this imputation method. The missing data at Week 52 for this study will be imputed using the linear extrapolation approach. Missing data are imputed by assuming historical placebo progression (11.39 points/year) in the 28-item PSPRS total score from the visit of the last observation prior to Week 52. For example, if a participant discontinues at Week 24 with 28-item PSPRS total score of 41 points, then the Week 52 value is imputed with $41 + 11.39 \cdot (1 - (24/52))$. The natural disease progression, 11.39 points/year in 28-item PSPRS and 9.34 points/year in 15-item PSPRS, were determined based on an analysis of subjects with PSP disease onset < 5 years from the Davunetide study. After all missing data have been imputed, an ANCOVA model adjusting for treatment group, baseline PSPRS, baseline Color Trails 2 test (≤ 170 or > 170 seconds) and region will be applied to analyze the change from baseline in PSPRS total score at Week 52.

5.2.4.4 Tipping point analysis

The tipping-point analysis is a progressive stress-testing to assess how severe departures from missing-at-random must be in order to overturn the conclusion of the primary analysis [Yan et al. 2009]. For our study, subjects are assumed to have worse scores after early withdrawal from study compared to subjects who remain on study.

The missing data are first imputed by the standard multiple imputation (assuming missing at random). To reflect the worse performance after early withdrawal, pre-specified shift parameters δ_c and δ_t (e.g., the difference between δ_c and δ_t is the observed treatment effect rounded up to the next integer) are added to the imputed values for subjects on placebo and BIIB092, respectively. The adjusted multiple imputed datasets will then be analyzed by an ANCOVA model and the results will be combined using the Rubin's rule for inference.

A range of shift parameters δ_c and δ_t will be applied and p-value will be presented for each combination of δ_c and δ_t . The tipping region is defined as the combinations of δ_c and δ_t such that the treatment effect is no longer significant (p-value greater than the significance level). Plot of tipping region for change from baseline in PSPRS at Week 52 will be presented.

The scientific plausibility of the tipping region will be evaluated. If implausible departures from the missing-at-random assumption (large δ) are needed in order to change the results from statistically significant to insignificant, the results of the primary analysis are considered to be robust to departure from the missing-at-random assumption.

5.2.4.5 Pattern mixture model

The pattern mixture model (PMM) represents a general and flexible framework to model the predictive distribution of missing data conditional on the observed data [Little 1993, 1994]. It allows formulating assumptions regarding missing data in a transparent and clinically interpretable manner.

In the PMM framework, subjects are grouped into missing patterns so that subjects in the same pattern share similar missingness characteristics. In this analysis, missing patterns will be defined according to the reasons for early withdrawal from study as reported on the electronic case report form (eCRF). The following two patterns will be considered:

- Subjects who withdraw due to reasons that may be related to efficacy, including lack of efficacy, subject request to discontinue study treatment, subject withdrew consent, poor/non-compliance, death and withdrawal by caregiver;
- Subjects who withdraw due to reasons that are unlikely related to efficacy, including adverse event, lost to follow-up, pregnancy, subject no longer meets study criteria, administrative reason by sponsor, and other.

Subjects who withdraw due to reasons that may be related to efficacy will be penalized and their missing data will be imputed using the copy increment from reference (CIR) method [Carpenter et al. 2013] (see Section 5.2.4.1 for description of the CIR method). Subjects who withdraw due to reasons that are unlikely related to efficacy will be handled using the missing-at-random assumption and their missing data will be imputed using the standard multiple imputation method [Rubin 1987]. Subjects with missing data due to reasons other than early withdrawal (such as item missing, out of window, etc.) will be handled using the missing-at-random assumption. For both imputation methods, the following covariates will be included in the imputation model: treatment group, baseline PSPRS, baseline Color Trails 2 test (≤ 170 or > 170 seconds), region and observed post baseline PSPRS total score (data from each visit as a covariate). Implementation details can be found in Section 11.2.3.

The imputed datasets will be analyzed by MMRM model described in Section 5.1. The analyzed results from the imputed datasets will be combined based on Rubin's rules [Rubin 1987] assuming that the statistics estimated from each imputed dataset are normally distributed.

If intermediate missing values are encountered (such as data missing at Week 12 but are available at subsequent visits), a Markov chain Monte Carlo (MCMC) method that assumes multivariate normality will be used to impute the intermediate missing values and produce a monotone missing pattern (data with only terminal missing and no intermediate missing) [Li 1988; Schafer 1997].

5.2.5 Supplementary analysis

5.2.5.1 PSPRS subscales and item level scores

The 28-item PSPRS is comprised of 6 subscales: History, Mentation, Bulbar, Ocular, Limb, and Gait. 28-item PSPRS is the sum of the scores for these 6 subscales. For each of the 6 subscales, the baseline value and the change from baseline at each post-baseline visit will be summarized by treatment group. The same MMRM model as the primary analysis will also be applied to the 6

subscales. A forest plot of adjusted mean change from baseline versus placebo at Week 52 from each subscale will be provided. A categorical summary of each of the 28 items will be performed.

The same summary and MMRM analyses will be applied to the 3 subscales of 15-item PSPRS, gait/limb function, ocular motor and bulbar. A categorical summary of each of the 15 items will also be performed.

5.2.5.2 PSPRS time to clinical outcome and shift analysis

Time to clinical outcome analysis will include the following clinical outcome definitions based on selected items in the 28-item PSPRS:

- Loss of independent walking: change from 0, 1, 2 or 3 at baseline to 4 at any post-baseline visits up to Week 52 in Item 26 Gait;
- Unintelligible speech: change from 0, 1, 2, or 3 at baseline to 4 at any post-baseline visits up to Week 52 in Item 12 Dysarthria;
- Unable to do activities of daily Living: change from 0, 1, 2 or 3 at baseline to 4 at any post-baseline visits up to Week 52 in Item 4 Using knife & fork, buttoning clothes, washing;
- Require use of feeding tube: change from 0, 1, 2 or 3 at baseline to 4 at any post-baseline visits up to Week 52 in Item 3 dysphagia solids or Item 13 dysphagia liquids;
- Any clinical outcome: meet any of the above four clinical outcomes.

Time to clinical outcome is defined as the time from the first dose to the first clinical outcome in the placebo-controlled period. Subjects who don't reach the clinical outcomes will be censored and the censoring date is the last date in the placebo-controlled period. Time to clinical outcome will be displayed by Kaplan-Meier plot by treatment group and also be analyzed using a Cox proportional hazards model adjusting for treatment group, baseline Color Trails 2 test (≤ 170 or > 170 seconds) and region.

With the recognition that death can often be directly related to the progression of PSP and the development of the clinical outcome under consideration, we will reanalyze the data using the time to clinical outcome or death as a composite outcome for each clinical outcome defined above.

Shifts from baseline to each score value at post baseline visits for individual item for all the 28 items in PSPRS will be presented. The same shift from baseline analysis will be applied to each item in the 15-item PSPRS.

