Phase 2b Study of BIIB092 in Participants with Progressive Supranuclear Palsy

██████████; LP = lumbar puncture; MDS-UPDRS = Movement Disorder Society-sponsored revision of the Unified Parkinson's Disease Rating Scale; MoCA = Montreal Cognitive Assessment; NSAE = non-serious adverse event; PK = pharmacokinetic; MRI = magnetic resonance imaging; NE = neurological examination; PSP = Progressive Supranuclear Palsy; PSPRS = Progressive Supranuclear Palsy Rating Scale; QoL = quality of life; RBANS = Repeatable Battery for the Assessment of Neuropsychological Disease Severity; ██████████; SAE = serious adverse events; SEADL = Schwab and England Activities of Daily Living scale; ██████████ WOCBP = women of childbearing potential.

- ^a Efficacy assessments requiring participant involvement should be completed prior to dosing with study treatment unless otherwise specified in the notes; specific attention should be paid to conducting the Week 24 MRI within 7 days prior to the Week 24 dosing visit. The study visits at Weeks 0, 12, 24, 36, 48, 52, and Early Discontinuation, which involve the conduct of efficacy assessments, may be completed over a period of up to 3 consecutive days.
- ^b Weeks 28, 32, 40, and 44 may qualify for a home visit if appropriate. See Section 5.1.4 for details.
- ^c Participants who discontinue study treatment during the double-blind period of the study (prior to Week 52) and remain enrolled in the study will be expected to complete scheduled safety and efficacy evaluations at Weeks 12, 24, 36, 48, and 52 until the decision is made to withdraw from the study.
- ^d Early Discontinuation visit procedures should be completed for any participant who discontinues study treatment and also withdraws from the study at any time prior to Week 52. Participants who withdraw from the study should be encouraged to return to the clinic at Week 52 to complete the Week 52 procedures. If the visit cannot be done in person by the participant, the site should attempt a phone call at approximately Week 52 to collect at a minimum vital status (whether the participant is alive or dead) and SAE/AE information on the participant.
- ^e This 30-day assessment of AEs/SAEs may be done by phone if no visit occurs.

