5 EFFICACY DATA

5.1 General Considerations

All efficacy analyses will be performed on the ITT population. In addition, the primary and the key secondary endpoints will also be performed on the PP population.

The primary, sensitivity and supplementary analyses for the primary and key secondary endpoints are listed in the below table.

Table 1 Analysis for Primary and Key Secondary Endpoints

| Endpoint | Analysis | Analysis Population | SAP Section |
|---|--|----------------------------|--------------------|
| 28-item PSPRS total score, 15-item PSPRS total score | Primary: Analysis of change from baseline at Week 52 (MMRM) | ITT | 5.2.3 |
| | Sensitivity: Copy increment from reference method (MMRM) | ITT | 5.2.4.1 |
| | Sensitivity: Jump to reference method (MMRM) | ITT | 5.2.4.2 |
| | Sensitivity: Imputation by natural disease progression (ANCOVA) | ITT | 5.2.4.3 |
| | Sensitivity: Tipping point analysis (ANCOVA) | ITT | 5.2.4.4 |
| | Sensitivity: Pattern mixture model (MMRM) | ITT | 5.2.4.5 |
| | Supplementary: PSPRS subscale analysis (MMRM) | ITT | 5.2.5.1 |
| | Supplementary: Time to clinical outcome analysis (Kaplan Meier analysis and Cox proportional hazard model) | ITT | 5.2.5.2 |
| | Supplementary: Censoring after intercurrent events (MMRM)* | ITT | 5.2.5.3 |
| | Supplementary: Per-protocol analysis (MMRM) | Per-protocol | 5.2.5.4 |
| | Supplementary: Responder analysis (Logistic regression) | ITT | 5.2.5.5 |

| | | | |
|---|---|--------------|---------|
| | Supplementary: Slope analysis (MMRM) | ITT | 5.2.5.6 |
| | Supplementary: Divergence effect analysis (MMRM) | ITT | 5.2.5.7 |
| MDS-UPDRS Part II, PSP cognitive composite battery, PSP-QoL | Primary: Analysis of change from baseline at Week 52 (MMRM) | ITT | 5.3.1.1 |
| | | | 5.3.1.3 |
| | | | 5.3.1.4 |
| | Sensitivity: Pattern mixture model (MMRM) | ITT | 5.3.1.5 |
| | Supplementary: Censoring after intercurrent events (MMRM)* | ITT | 5.3.1.5 |
| | Supplementary: Per-protocol analysis (MMRM) | Per-protocol | 5.3.1.5 |
| | Supplementary: Slope analysis (MMRM) | ITT | 5.3.1.5 |
| Supplementary: Divergence effect analysis (MMRM) | ITT | 5.3.1.5 | |
| Supplementary: Subscale analysis for PSP cognitive composite battery (MMRM) | ITT | 5.3.1.5 | |
| CGI-C | Primary: Analysis at Week 52 (MMRM) | ITT | 5.3.1.2 |
| | Sensitivity: Pattern mixture model (MMRM) | ITT | 5.3.1.5 |
| | Supplementary: Censoring after intercurrent events (MMRM)* | ITT | 5.3.1.5 |

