5.1.3 Considerations for multiple comparison adjustments

Key secondary endpoints have been rank prioritized, in the order shown in Section 2. In order to control for a Type I error for the key secondary endpoints, a sequential closed testing procedure will be used. If statistical significance is not achieved for a key secondary endpoint, all key secondary endpoint(s) of a lower rank will not be considered statistically significant.

There will be no multiple comparison adjustments for the sensitivity or supplementary analyses for the primary and key secondary efficacy endpoints, the non-key secondary endpoints, the tertiary efficacy endpoints, the subgroup analyses or the additional analyses.

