6.3.1 Quantitative analyses

Actual values, change from baseline and percent change from baseline will be summarized by visit for hematology, blood chemistry, coagulation (INR and prothrombin time), and the urinalysis parameters specific gravity and pH (actual values over time only). Number of evaluable subjects, mean, standard deviation, median, 25% and 75% quartiles, minimum and maximum values will be presented at each visit. Plots of mean values (with standard error) for actual values at each visit will be provided; mean values at timepoints where n < 20 will not be plotted.

Visit windows for by visit summaries

For laboratory by visit summaries, the analysis visit should be defined using visit windows (see Table 8).

Table 8 Visit Windows for Laboratory by Visit Summaries

| Analysis visit | Target visit day | Analysis visit window |
|---|------------------|--|
| Baseline | 1 | Most recent non-missing pre-dose value |
| Week 4 | 29 | [1 (post-dose only), 42] |
| Week 8 | 57 | [43, 70] |
| Week 12 | 85 | [71, 126] |
| Week 24 | 169 | [127, 210] |
| Week 36 | 253 | [211, 294] |
| Week 48 | 337 | [295, 350] |
| Week 52 | 365 | [351, the end day of the placebo-controlled period*] |
| * The end day of the placebo-controlled period is the last day before the first dose in OLE for subjects who enter OLE, and is the last day in study for subjects who do not enter OLE. | | |

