6.4 ECGs

All individual values for QT interval, QT interval corrected for heart rate by Bazett's formula (QTcB), and QT interval corrected for heart rate by Fridericia's formula (QTcF) will be presented in the data listings. QT, QTcB, and QTcF will also be included in the summary statistics.

All available non-missing values of ECG parameters should be used in the listings, summaries, and analyses for the double-blind and open-label treatment periods. However, if QTcF is missing and RR interval in seconds is available, then QTcF will be calculated as

$$QTcF = \frac{QT}{RR^{1/3}}$$

If both QTcF and RR in seconds are missing, then QTcF will be calculated as

$$QTcF = \frac{QT}{(60/HEART\ RATE)^{1/3}}$$

Although all recorded ECG parameter values, including abnormal ECG findings, will be included in the data listings, only quantitative values recorded at or near scheduled time points will be included in the summary statistics (see Table 10).

Table 10 Visit Windows for ECG

| Analysis visit | Target visit day | Analysis visit window |
|---|------------------|---|
| Baseline | 1 | Most recent non-missing pre-dose value |
| Week 24 | 169 | [1 (post-dose only), 266] |
| Week 52 | 365 | [267, the end day of the placebo-controlled period *] |
| * The end day of the placebo-controlled period is the last day before the first dose in OLE for subjects who enter OLE, and is the last day in study for subjects who do not enter OLE. | | |

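### Time-to-clinical-outcome analysis: censoring should stop at the last PSPRS rating, because the stated end-of-period date can count unscored time as event-free

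*SAP*

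**What the plan says.** Placebo-controlled SAP, Section 5.2.5.2, defines four outcomes and their combination from 28-item PSPRS scores. Loss of independent walking, for example, is a "change from 0, 1, 2 or 3 at baseline to 4 at any post-baseline visits up to Week 52 in Item 26 Gait". Participants who reach no outcome "will be censored and the censoring date is the last date in the placebo-controlled period". The section does not define that date and does not refer to the last rating. The data are then reanalysed with outcome or death as a composite, for which no separate censoring rule is given.

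Elsewhere the same SAP defines the date per participant, in footnotes to the laboratory, ECG and anti-drug-antibody visit windows (Tables 8, 10 and 13): "The end day of the placebo-controlled period is the last day before the first dose in OLE for subjects who enter OLE", and it "is the last day in study for subjects who do not enter OLE". Section 4.3 also uses a participant-level end date for duration of follow-up. None of these places says which contact sets the last day in study.

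Protocol Table 2 schedules the PSPRS at Weeks 0, 12, 24, 36, 48, 52 and Early Discontinuation. Footnote c keeps participants who stop treatment on the rating schedule. Footnote d asks for the Early Discontinuation visit at withdrawal and encourages a return at Week 52. Failing that, "the site should attempt a phone call at approximately Week 52" for vital status and adverse events.

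The analysis is listed as supplementary in SAP Table 1. Section 5.1.3 adds: "There will be no multiple comparison adjustments for the sensitivity or supplementary analyses".

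**The concern.** Time at risk should end where detection ends. A participant who is not being rated cannot be recorded as having an item score of 4, yet the stated rule keeps that person in the risk set as event-free until the end date. If one arm has more such time, its estimated hazard is diluted and the hazard ratio moves in its favour with no treatment effect.

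The protocol produces several contacts without a rating that a programmer could take as the last day: the Week 52 call, the call about 30 days after stopping treatment (Section 8.2), and the last known alive date for participants lost to follow-up (Section 8.4). Section 8.3 exempts participants who refuse further contact from the exit visit. A participant with no post-baseline rating at all would also count as event-free up to the end date.

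**Working it through.** **Inputs from the documents.** Allocation is 306 to 153, overall dropout is about 25% with no split by arm, and ratings fall at Weeks 12, 24, 36, 48, 52 and at exit. The SAP and protocol state no event rate, event count or power for this analysis. The only stated power is for the primary endpoint, and it reproduces: 3.2 / (9.95 × √(1/230 + 1/115)) = 2.816, which on 343 degrees of freedom gives 80.2% against the stated 80%.

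**Assumptions.** True hazard ratio 1; 52-week outcome risk 10%, 20% or 40%; withdrawal (BIIB092/placebo) 25/25, 30/15, 30/20 or 20/35; exit rating done for all, half or none of the withdrawals. Death was not modelled as a competing event.

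**Step 1: date = own last day in study.** The Cox model compares risk sets only at event times, and event times are rating dates. Someone who leaves between two scheduled ratings is out of the risk set before the next one, whether censored at the last rating or at the leaving date. Simulation of 45 scenarios, including 10% missed visits at random and a three-fold withdrawal hazard after the outcome, changed the hazard ratio by at most 0.002. The unscored gap is zero if the exit rating is done and averages about 5.7 weeks among event-free withdrawers if none has one.

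**Step 2: date = Week 52 contact.** Everyone without an event now stays in the risk set to Week 52. With a true hazard ratio of 1, the estimate is then roughly the ratio of the scored shares of the year, f. For withdrawal proportion w at constant hazard:

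- With exit ratings, f = w / (−ln(1 − w)). This is 0.8411 at 30%, 0.8963 at 20% and 0.9230 at 15%. The ratios are 0.8411/0.8963 = 0.94 and 0.8411/0.9230 = 0.91.
- Without exit ratings, f = Σ (interval/52) × (1 − w)^(visit week/52). This is 0.8084, 0.8745 and 0.9066. The ratios are 0.92 and 0.89.

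Simulation agrees:

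| Withdrawal, BIIB092/placebo | Censored at last PSPRS | Censored at Week 52 |
|---|---|---|
| 25/25 | within about 1% of 1 | same, within 0.002 |
| 30/20 (one assumed hazard, 0.35 per year) | 1.02 | 0.95 |
| 30/15 | 0.99–1.03 | 0.88–0.92 |
| 20/35 | 0.97–1.01 | 1.09–1.15 |

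The shift due to the date is 1 − 0.95/1.02 = 7% at 30/20. At 30/15 it is 1 − 0.922/1.034 = 11% to 1 − 0.876/0.990 = 12%. With a three-fold withdrawal hazard after the outcome and no exit ratings, the 30/15 estimate reached 0.87, or 13% below 1. About 3 points of that come from informative withdrawal, since censoring at the last PSPRS already gave 0.96–0.97.

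In trials of 306 and 153 at outcome risks of 20% and 40%, one-sided false positives (nominal 2.5%) towards the arm with more withdrawals were 5.9–12.2% at 30/15 and 5.1–12.0% at 20/35 under the Week 52 date. Under the last day in study they were 1.3–2.8%.

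**Step 3: final ratings missed while still enrolled, 10% versus 5%.** At those visits the scored fraction is 0.90 against 0.95, a deficit of 1 − 0.90/0.95 = 5.3%. It applies only to the share of outcomes first recorded there. With 25% withdrawal in both arms and no exit ratings:

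- Week 52 contributes (4/52) × 0.75 = 0.0577.
- Week 48 contributes (12/52) × 0.75^(48/52) = 0.1769.
- Week 36 contributes (12/52) × 0.75^(36/52) = 0.1891.
- The total over all visits is 0.8418.

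| Ratings missed | Share of outcomes | Shift in hazard ratio |
|---|---|---|
| Week 52 | 6.9% | 0.4% |
| Weeks 48 and 52 | 27.9% | 1.5% |
| Weeks 36, 48 and 52 | 50.3% | 2.6% |

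Simulation gave 0.3%, 1.3% and 2.4%. The figure of about 2% therefore means that the last two or three ratings are missed, not Week 52 alone.

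**The case against.** The strongest reply is that the SAP does define the end of the period per participant, three times, and that the protocol rates withdrawers at exit and keeps rating those who only stop treatment. On that reading Step 1 applies and nothing moves. Most of this stands.

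A reader might infer that the rule as written favours the arm with more withdrawals. The documents do not support that. They give no dropout by arm, equal withdrawal alone produces no shift, and no passage makes a call after withdrawal the last day in study. The call is itself a fallback for people first asked to return for the Week 52 procedures, which include the PSPRS. When exit ratings are done, either rule tilts about 2–4% against the arm with more withdrawals, because that arm gets extra chances of detection.

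A further fair objection concerns the composite. Counting deaths after the last rating while censoring survivors at their last rating makes follow-up depend on outcome. That cannot be removed by choice of date alone, because vital status is collected without a PSPRS, so the rule adopted should say so openly.

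What remains is that Section 5.2.5.2 neither cross-refers to the footnote definition nor says which contact counts. The participant-level definition also does not cover ratings missed at the end of follow-up while still enrolled.

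**Conclusion.** The point holds as a gap in specification with a conditional bias. The rule permits event-free time in which no outcome could be seen. Withdrawals handled by the participant-level date change the hazard ratio by at most 0.002. Final ratings missed by 10% versus 5% of enrolled participants change it by about 2%. A Week 52 contact used as the date gives about 7–13% at 30% versus 15–20% withdrawal, the top of that range including some effect of informative withdrawal. The direction depends on which arm has more unscored time, and the arm-specific rates and outcome risks are assumptions.

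Neither censoring rule cures informative withdrawal. Severity is minor: the analysis is supplementary and outside the alpha-controlled sequence, and the primary PSPRS comparison is unaffected.

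**What to change.** In Section 5.2.5.2 of the placebo-controlled SAP:

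- Censor participants without the outcome at their last PSPRS with the relevant item scored, on or before the end of the placebo-controlled period, and at day 1 if there is no post-baseline PSPRS.
- State that phone or vital-status contacts do not extend follow-up for the PSPRS outcomes.
- Give the outcome-or-death composite its own rule: deaths in the placebo-controlled period are events, and all others without the outcome are censored at the last PSPRS. Acknowledge that deaths after the last rating are counted while later time known alive is not.

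The cost is a few lines of text and one derivation, with no new data. The downside is slightly less person-time.

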5.1.4 Considerations for base MMRM model for change from baseline analyses

The observed value and change from baseline for a parameter of interest will be summarized by treatment group at each post-baseline visit. A mixed model repeated measures (MMRM) model will be used as the primary analysis to analyze change from baseline using fixed effects of treatment group, time (categorical), treatment group-by-time interaction, baseline for the parameter of interest, (baseline for the parameter of interest) by time interaction, baseline Color Trails 2 test (≤ 170 or > 170 seconds) and region (see healthcare region definitions in Section 3.1). An unstructured covariance matrix will be used to model the within-subject variance-covariance errors. If the unstructured covariance structure matrix results in a lack of convergence, the heterogeneous Toeplitz covariance structure followed by the heterogeneous first-order autoregressive covariance structure will be used. The Kenward-Roger approximation will be used to estimate the denominator degrees of freedom. If the unstructured variance-covariance structure does not converge in the MMRM model and a structured model is used, the sandwich estimator will be used to get the variance of the treatment effect estimator. The adjusted mean of each treatment group, as well as the treatment group differences will be displayed with 95% CI and p-value. In the primary analysis of each endpoint, missing data are assumed to be missing at random [Rubin 1976].

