5.2.5.5 Responder analysis

To further assess whether subjects on BIIB092 progress differently from those on placebo, responder analysis will be conducted. The responders will be determined by a threshold of the primary endpoint, i.e., subjects whose change from baseline PSPRS at Week 52 is smaller than or equal to the threshold will be classified as responders (not worsening) and otherwise will be classified as non-responders (worsening). All subjects with missing data at Week 52 will be classified as non-responders.

The responder analysis will be conducted for two threshold values i.e., subjects whose change from baseline in 28-item PSPRS at Week 52 are less than or equal to the threshold values. The number of responders and the response rate will be summarized by treatment group. The dichotomized response, responder vs. non-responder, will be modeled using a logistic regression adjusting for the following variables: treatment group, baseline PSPRS, baseline Color Trails 2 test (≤ 170 or > 170 seconds) and region. In addition to the two selected threshold values, the continuous responder curve that displays the percentage of responders under a wide range of threshold values will be presented by treatment group. The same analyses will be applied to 15-item PSPRS total score using two other threshold values. The threshold values determined using anchor- and distributed-based methods on Davunetide study data are: 6 points and 11 points for 28-item PSPRS change score; 4 points and 9 points for 15-item PSPRS change score.

Since all missing data will be considered as non-response, which is a special form of missing-not-at-random, this analysis can provide additional insights for the robustness of the primary analysis results.

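### The supplementary Cox models for time to clinical outcome leave out baseline PSPRS severity, which the SAP's other PSPRS models include; the test is valid but may lose power

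*SAP*

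**What the plan says.** Section 5.2.5.2 of the placebo-controlled SAP defines four clinical outcomes on PSPRS items (walking on item 26, speech on item 12, daily activities on item 4, feeding tube on items 3 or 13), plus the occurrence of any of them. Walking is typical: "change from 0, 1, 2 or 3 at baseline to 4 at any post-baseline visits up to Week 52 in Item 26 Gait". Participants who do not reach the outcome "will be censored and the censoring date is the last date in the placebo-controlled period". Each outcome is "analyzed using a Cox proportional hazards model adjusting for treatment group, baseline Color Trails 2 test" category and region. Each is then repeated as a composite with death.

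The SAP's other models for PSPRS include its baseline value:

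- Base MMRM (5.1.4): "baseline for the parameter of interest, (baseline for the parameter of interest) by time interaction"
- Natural-progression analysis (5.2.4.3): "an ANCOVA model adjusting for treatment group, baseline PSPRS, baseline Color Trails 2 test"
- Responder analysis (5.2.5.5): "logistic regression adjusting for the following variables: treatment group, baseline PSPRS, baseline Color Trails 2 test"
- Slope model (5.2.5.6): baseline PSPRS and its interaction with time

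Table 1 lists the time-to-outcome analysis as supplementary, in the ITT population. Section 5.1.3 applies no multiplicity adjustment to it.

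**The concern.** A participant who starts at 3 on the defining item is one point from the event; one who starts at 0 is four points away. The baseline item score is therefore built into the event definition, yet neither it nor any other PSPRS severity measure is in the model. The SAP gives no reason for departing from its own practice here. The sections on baseline characteristics (4.2) and subgroups (5.5) already single out gait item 26 at baseline, split at 3.

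Two things are at stake. In a Cox model, omitting a prognostic covariate moves the treatment hazard ratio toward 1, relative to the ratio conditional on that covariate, and tends to reduce power even when randomisation has balanced the arms. Separately, a participant already at 4 on a single defining item cannot meet that outcome, but nothing in 5.2.5.2 removes that person from the risk set.

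**Working it through.** **The plan's own figure.** The only stated power is for the primary endpoint (Protocol 17.1): 230 vs 115 completers, difference 3.2, SD 9.95, two-sided 0.05. The standard error is 9.95 × √(1/230 + 1/115) = 1.136. Then 3.2/1.136 = 2.816, and Φ(2.816 − 1.960) = 80.4% (80.2% with the t distribution). The stated 80% reproduces, but it says nothing about the Cox models, for which no event count, hazard ratio or power is given. Everything below therefore rests on assumptions.

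**Common set-up.** 306 vs 153 participants, 25% exponential dropout, events read at Weeks 12, 24, 36, 48 and 52, Efron ties. The SAP model (treatment, CTT 2 category, region) is compared with the same model plus one baseline severity covariate.

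**Simulation A: severity as a continuous covariate.** True conditional hazard ratio 0.65; severity correlated 0.3 with the variable behind CTT 2; 600 trials per cell. Each cell shows the hazard ratio and then the power, SAP model → with severity.

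| Severity HR per SD | Placebo events 15% | 30% | 50% |
|---|---|---|---|
| 1.00 (e^0) | 0.651→0.651; 28.5→27.8% | 0.648→0.647; 55.2→54.5% | 0.649→0.648; 76.7→76.3% |
| 1.49 (e^0.4) | 0.657→0.652; 33.2→31.3% | 0.644→0.637; 53.5→54.5% | 0.658→0.648; 73.7→75.2% |
| 2.01 (e^0.7) | 0.671→0.660; 29.7→30.5% | 0.670→0.650; 47.3→53.3% | 0.686→0.654; 64.8→75.8% |
| 2.72 (e^1.0) | 0.662→0.638; 28.5→34.7% | 0.680→0.646; 44.7→56.5% | 0.701→0.653; 63.5→76.0% |
| 4.48 (e^1.5) | 0.697→0.637; 25.3→33.3% | 0.739→0.660; 35.0→52.5% | 0.750→0.676; 44.7→69.0% |

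Monte Carlo error is about 2 points: √(0.5 × 0.5/600) = 0.020. An uninformative covariate costs under 1 point (first row). A weak one gains nothing detectable. From 2.01 to 4.48 per SD the gain runs from 0.8 to 24.3 points.

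**Simulation B: events built from the item score.** A latent item score progresses from its baseline value, and the event is reaching 4. Mean progression is 0.41 points a year (11.39 points a year from SAP 5.2.4.3, divided by 28 items) or an assumed faster 0.8. Treatment slows it by 28% (3.2/11.39 = 0.281) or by 50%. 800 trials per row.

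| Baseline 0/1/2/3 (%) | Points/year | Slowing | Events | HR | Power |
|---|---|---|---|---|---|
| 10/30/35/25 | 0.41 | 28% | 44 | 0.786→0.739 | 12.8→17.6% |
| 10/30/35/25 | 0.8 | 28% | 74 | 0.718→0.648 | 29.9→44.1% |
| 5/20/35/40 | 0.8 | 28% | 111 | 0.739→0.682 | 33.3→50.7% |
| 10/30/35/25 | 0.41 | 50% | 39 | 0.625→0.567 | 30.7→41.1% |
| 10/30/35/25 | 0.8 | 50% | 63 | 0.518→0.432 | 71.9→88.0% |
| 5/20/35/40 | 0.8 | 50% | 95 | 0.546→0.472 | 85.5→94.8% |

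Gains run from 4.8 to 17.4 points. Two further settings with most participants starting at 0 or 1 gave only 8 to 10 events (6.9→11.4% and 10.3→17.0%). The item coefficient there was so large that the fits are close to separation, so I do not lean on them. Item measurement error was set low (SD 0.15), which makes the baseline score strongly prognostic by construction.

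**A modest effect.** With hazard ratio 0.72, severity 2.0 per SD, CTT 2 in both models and 400 trials per setting, power moved 41→49% at about 33% placebo events, 28→30% at 20% and 14→16% at 10%. The last two changes are within simulation error.

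**Type I error.** With no treatment effect (2,000 trials each), rejection rates were 4.3% and 4.1% for the SAP model and 4.7% and 4.1% with severity added.

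**The case against.** A fair defence is that the planned model adjusts for the randomisation factors (region standing in for country), was prespecified, and belongs to a supplementary analysis for which no power was promised. All of that stands.

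A reader might infer that the planned hazard ratio is biased. It is not. Because the hazard ratio is non-collapsible, the planned model estimates a valid but less conditional quantity, and its type I error holds. That defence does not explain why the model conditions on CTT 2 and region but not on baseline severity, and the SAP states no estimand for this analysis that would settle it.

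A reader might also infer that a large power loss is established. The documents contain nothing that fixes event rates or prognostic strength, and for the rarer single outcomes the gain could be negligible.

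Nor does the point support adding every defining item together with the total. Feeding tube has two items and any clinical outcome has five, the total contains all of them, and events may be few.

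On the risk set, 5.2.5.2 does not say in terms who is at risk; keeping participants who start at 4 is an inference from the ITT population and the censoring rule. Protocol 6.1.2 requires the ability to take at least 10 steps with limited help, so few should start at 4 on the gait item. The number affected on the other items is unknown.

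**Conclusion.** The omission is plain in the text and inconsistent with the SAP's other PSPRS models. It leaves the test valid, but it gives a hazard ratio nearer 1 than the severity-adjusted one and can lose power. The loss is about nil for a weak covariate or few events and roughly 5 to 17 points when events are built from the item score. The 24-point figure needs a severity hazard ratio of 4.48 per SD and half the placebo group having events, so it should not be read as expected. All sizes depend on assumed event rates, effects and prognostic strengths. Neither the primary analysis, which already adjusts for baseline PSPRS, nor the conclusion drawn from it is affected. This is an inexpensive precision improvement, not the correction of an invalid analysis.

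**What to change.** Before unblinding, add one prespecified baseline severity covariate to each Cox model in 5.2.5.2:

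- **Walking, speech, daily activities (without death):** the baseline score of the defining item (26, 12 or 4).
- **Feeding tube, any clinical outcome, and all composites with death:** the baseline 28-item PSPRS total.

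For the three single-item outcomes without death, restrict the risk set to participants scoring 0-3 on that item at baseline. Keep everyone in the composites with death, since a participant already at 4 can still die.

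The cost is a few lines of SAP text and one more parameter in models that may have few events. Baseline PSPRS is already collected at Week 0 (Protocol Table 2). If the covariate turns out to be uninformative, the simulated loss is under 1 point of power.
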